### **10.5.3 Overall Survival (Arm A versus Arm C and Arm B versus Arm C)**

OS will be analyzed by Kaplan-Meier methodology and compared between Arm A and Arm C as well as between Arm B and Arm C using a two-sided log-rank test stratified by LDH level. Median survival time for all three arms will be calculated and corresponding 80% confidence intervals will be presented. Hazard ratio estimates (Arm A versus Arm C, Arm B versus Arm C) and their corresponding 80% confidence intervals will be obtained from a Cox proportional hazards model stratified by LDH level.

## **10.6 Tertiary Efficacy Analyses**

### **10.6.1 Duration of Overall Response**

The distribution of DOR will be estimated for each treatment arm using Kaplan-Meier methodology. Median DOR will be estimated and an 80% confidence interval will be presented for each treatment arm.

### **10.6.2 Progression-Free Survival (Arm A versus Arm B)**

A hazard ratio estimate of Arm A vs. Arm B and the corresponding 80% confidence interval will be obtained from a Cox proportional hazards model stratified by LDH level.

### **10.6.3 Overall Survival (Arm A versus Arm B)**

Hazard ratio estimate of Arm A vs. Arm B for OS and the corresponding 80% confidence interval will be obtained from a Cox proportional hazards model stratified by LDH level.

#### **10.6.4 ECOG Performance Status (Arm A vs Arm C and Arm B vs Arm C)**

Mean Change (80% CI) from baseline to each scheduled post-baseline visit (as defined in [Table 2](#)) will be compared between Arm A and Arm C as well as between Arm B and Arm C using ANCOVA with treatment arm as a factor and baseline ECOG value as a covariate.

Subjects that do not have a baseline measurement or do not have any post-baseline measurements will not be included. Post-baseline measurements will be excluded after 30 days of the last dose of veliparib/placebo (including both combination period and maintenance period), carboplatin, or etoposide, whichever occurs the last.

#### **10.7 Efficacy Subgroup Analysis**

To evaluate the impact of demographic and baseline characteristics on efficacy, subgroup analyses may be performed for OS and PFS between Arm A and Arm C, and presented in forest plots with hazard ratio estimate (80% CI) using Cox proportional hazard model for each subgroup. Subgroups defined below may be used for the subgroup analyses:

1. Schlafen-11 (SLFN11) expression (+, –) via IHC
2. LP-52 biomarker status (+, –) as determined by HTG technology
3. Gender (Male, Female)
4. Age (< 65 years, ≥ 65 years)
5. Region (US, EU, and the rest of world)
6. Baseline ECOG performance status (0, 1)
7. Smoking history (current smoker, never smoked, and past smoker as defined in Section 8.1.1.1 in protocol)
8. LDH (> ULN, ≤ ULN) based on IVR for the stratification factor

9. Four cross-over subgroups per gender and LDH categories (LDH > ULN in male, LDH > ULN in female, LDH ≤ ULN in male, LDH ≤ ULN in female)
10. Number of metastatic sites (1, ≥ 2)

## **10.8 Additional Efficacy Analysis**

The following additional efficacy analysis may be performed:

1. Modified PFS analysis for Arm A & Arm C to consider the initiation of any anti-cancer post-treatment therapy as an event.
2. Modified ORR analysis for Arm A & Arm C and DOR analysis for all 3 arms where both confirmed and unconfirmed responses are to be considered.

## **11.0 Safety Analysis**

### **11.1 General considerations**

All safety analyses will be performed on Phase 2 AST population, and will be summarized by each treatment arm (A & B & C) for combination period alone. Safety analyses will include all data in the extracted database (no cutoff). For visit-wise safety analyses, the analysis visit widows as described in [Table 2](#) will be used to align data. There will be no statistical comparison for safety analysis unless otherwise specified.

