#### **8.1.7.2 Adverse Events**

Analyses of adverse events will include only "treatment-emergent" events, i.e., those that have an onset on or after the day of the first dose of study drug (veliparib or placebo). Analyses will not include those that have an onset greater than 30 days after the last dose of study drug.

Treatment-emergent adverse events will be coded and summarized by system organ class and preferred term according to the Medical Dictionary for Regulatory Activities (MedDRA) adverse event coding dictionary. The percentage of subjects experiencing an adverse event at a given NCI CTCAE version 4.0 grade, and relationship to study drug will be provided. For Phase 1, all summaries will be done by dose level. For Phase 2, comparisons of the percentages of subjects experiencing an adverse event between Arm A and Arm C as well as between Arm B and Arm C will be performed using Fisher's exact test.

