#### **8.1.7.3 Serious Adverse Events**

Serious adverse events will be summarized using the same methods as adverse events described above in Section [8.1.7.2](#).

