## **4.0 Study Objectives, Design and Procedures**

### **4.1 Objectives**

The primary objective of the study is to evaluate if the addition of veliparib in combination with carboplatin and etoposide followed by veliparib maintenance monotherapy results in improved progression free survival (PFS) versus placebo in combination with carboplatin and etoposide followed by placebo monotherapy in subjects with treatment-naïve ED SCLC.

The secondary objectives of the study are to evaluate (1) if veliparib in combination with carboplatin and etoposide followed by placebo monotherapy results in improved PFS versus placebo in combination with carboplatin and etoposide followed by placebo monotherapy in subjects with treatment-naïve ED SCLC; (2) if veliparib in combination with carboplatin and etoposide results in improved objective response rate (ORR) versus placebo in combination with carboplatin and etoposide, at the time of completion of maintenance therapy, or completion of combination therapy if subject was not involved in maintenance phase. In protocol v.5 dated 22 NOV 2016, Chapter 4.0, objective response rate is to be evaluated by the combination therapy for all subjects. We modified the analysis period by adding maintenance phase following ITT (intent-to-treat) population principle to avoid observation bias; (3) if veliparib in combination with carboplatin and etoposide followed by veliparib maintenance monotherapy results in improved overall survival (OS) versus placebo in combination with carboplatin and etoposide followed by placebo monotherapy; (4) if veliparib in combination with carboplatin and etoposide followed by placebo monotherapy results in improved OS versus placebo in combination with carboplatin and etoposide followed by placebo monotherapy; (5) to further evaluate the safety of veliparib in combination with carboplatin and etoposide followed by veliparib maintenance monotherapy.

The tertiary objectives are to (1) evaluate if veliparib in combination with carboplatin and etoposide followed by veliparib maintenance monotherapy results in improved duration of overall response (DOR) versus placebo in combination with carboplatin and etoposide

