### **11.2 Analysis of Adverse Events**

Analyses of adverse events will include only "treatment-emergent" events (TEAE), i.e., those that have an onset (worst CTC grade) prior to or on the 30 days of last dose of study drug in combination period. TEAEs will be coded and summarized by preferred term according to the Medical Dictionary for Regulatory Activities (MedDRA) adverse event coding dictionary. Subjects reporting more than one AE will be counted only once in the overall analysis. Summary data by each treatment arm will be presented by but not limited to the following statistics:

- The numbers and percentage of subjects experiencing any TEAE;
- The numbers and percentage of subjects experiencing grade 3 or 4 TEAEs;
- The numbers and percentage of subjects experiencing TEAEs that investigator found having a reasonable possibility related to veliparib/placebo;
- The numbers and percentage of subjects experiencing grade 3 or 4 TEAEs that investigator found having a reasonable possibility related to veliparib/placebo;
- The numbers and percentage of subjects experiencing TEAEs that led to study discontinuation due to disease progression or not due to disease progression;
- The numbers and percentage of subjects experiencing TEAEs that led to veliparib/placebo/carboplatin/etoposide discontinuation due to disease progression or not due to disease progression;
- The numbers and percentage of subjects experiencing TEAEs that led to veliparib/placebo/carboplatin/etoposide reduction, interruption, or delay. If an AE led to more than one actions, consider them as one;
- The numbers and percentage of subjects experiencing any serious TEAE;
- The numbers and percentage of subjects experiencing any serious TEAE that investigator found having a reasonable possibility related to veliparib/placebo;
- The numbers and percentage of subjects experiencing any TEAE of special interest;
- The numbers and percentage of subjects experiencing any grade 3 or 4 TEAE of special interest;
- Listing of TEAEs that led to death;
- The numbers and percentage of subjects experiencing TEAEs that led to death;
- The numbers and percentage of subjects experiencing TEAEs that led to death that investigator found having a reasonable possibility related to veliparib/placebo;

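### SAP 11.1-11.2 confines AE and SAE tables to the combination period, an undeclared departure from the protocol that leaves most or all of maintenance without AE or SAE rates

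*SAP*

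**What the plan says.** **SAP.** Section 11.1 states that all safety analyses "will be summarized by each treatment arm (A & B & C) for combination period alone". Section 11.2 limits AE analyses to treatment-emergent events, defined as "those that have an onset (worst CTC grade) prior to or on the 30 days of last dose of study drug in combination period". It gives no start date. The serious, special-interest and fatal AE summaries listed there are all counts of treatment-emergent events, so they share this window. Section 6.0 defines a last-dose date for the maintenance period, but the AE window does not use it.

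**Protocol.** Section 8.1.7.2 starts the AE window at the first dose of veliparib or placebo and sets the upper limit as follows: "Analyses will not include those that have an onset greater than 30 days after the last dose of study drug". For SAEs, Section 8.1.7.3 says "Serious adverse events will be summarized using the same methods as adverse events described above". The protocol does not mention maintenance here. Its inclusion follows from study drug being veliparib or placebo, which is given until progression or unacceptable toxicity (Synopsis, Duration of Treatment; Section 5.5.1).

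**Objective.** SAP 4.1 lists as its fifth secondary objective "to further evaluate the safety of veliparib in combination with carboplatin and etoposide followed by veliparib maintenance monotherapy". The same section openly states and explains a change to the ORR analysis period. Nothing similar appears for safety.

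**The concern.** Arms A and B have the same planned regimen until maintenance (SAP 4.2). Tables that stop at the combination period therefore cannot show what veliparib maintenance adds to toxicity, yet secondary objective 5 names that maintenance. A programmer who follows the SAP would drop AEs and SAEs that the protocol says will be analysed, and a reader would find no explanation.

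The final tables are also the only by-arm AE summary still planned. The DMC review used a data cutoff of 25 August 2017, and SAP 4.4 records that no further review was thought necessary before database lock.

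**Working it through.** The plan states no figure for how much of maintenance its AE window covers. The check is a comparison of texts, followed by calendar arithmetic on the dosing schedule.

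**1. Windows side by side**

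| | Start | End |
|---|---|---|
| Protocol 8.1.7.2-8.1.7.3 | first veliparib/placebo dose | 30 days after last dose of study drug |
| SAP 11.2 | not stated | 30 days after last combination-period dose |
| SAP 11.1, read literally | not stated | end of combination period |

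The SAP supports two readings. Under SAP 11.2 the 30-day tail runs into maintenance. Under SAP 11.1 it does not, and the combination-period exposure calculations in SAP 9.0 likewise use only data from before maintenance.

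**2. Reach of the 30-day tail.** Inputs: 21-day cycles, veliparib/placebo on Day -2 to 12, 4 to 6 cycles (Protocol 5.1 and 5.5.1). Count Cycle 1 Day -2 as day 1, with no Day 0.

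- Last combination dose = (n - 1) × 21 + 14, which is day 77 for n = 4 and day 119 for n = 6.
- Window closes 30 days later, on day 107 or day 149.
- The documents do not fix the maintenance start. Assume n × 21 + 1 to n × 21 + 3, that is Day 20 to 22 of the last cycle: days 85-87 or 127-129.
- Maintenance days covered = 107 - 87 + 1 = 21 to 107 - 85 + 1 = 23. Six cycles gives the same.
- With the 2-day window for the first maintenance visit (Protocol 5.3.1.1): 19 to 25.
- After a 21-day toxicity delay (Protocol 5.7): 0 to 2, or 0 to 4 with the visit window.

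**3. Planned veliparib dose** (SAP Tables 3 and 4)

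- Combination: 480 mg × 14 = 6,720 mg per cycle.
- Maintenance: 800 mg × 21 = 16,800 mg per 21 days, a ratio of 16,800 / 6,720 = 2.5.
- Four combination cycles total 26,880 mg, and 26,880 / 800 = 33.6, so planned maintenance dose passes that total after 34 days. Six cycles total 40,320 mg, and 40,320 / 800 = 50.4, so 51 days.

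Dose alone does not rank toxicity, because combination cycles also contain chemotherapy.

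**4. Share of maintenance time outside the tail (illustration only).** Time on maintenance is not in the documents. If it is exponential, the share of person-time outside is exp(-d / mean), with mean = median × 30.44 / ln 2 and d = 25 to 19 days.

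| Assumed median on maintenance | Share outside |
|---|---|
| 1 month | 57-65% |
| 3 months | 83-87% |
| 8.7 months (5.5 / 0.63, from SAP 4.3) | 94-95% |

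With d = 0 (SAP 11.1 read literally) the share is 100%.

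**5. What is still reported for maintenance.** Exposure and dose intensity (SAP 9.0), reasons for stopping (SAP 8.0), all deaths with causes (SAP 11.3) and Grade 3-4 laboratory listings (SAP 11.4). None of these gives an AE or SAE rate.

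**6. Related points of lower weight.** SAP 11.3 has no category for deaths on study drug, unlike Protocol 8.1.7.4. Its first category merges on-drug deaths with off-drug deaths within 30 days, and its later category mixes deaths on maintenance with deaths off drug. The laboratory window is also unclear. SAP 11.4 first cuts at the last combination dose, then ties the last dose to each analysis period, then refers to the last study drug. The final value in SAP 6.0 runs through maintenance.

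**The case against.** The strongest reply is that SAP 11.2 is the specific AE definition and should override the general sentence in 11.1. On that reading some maintenance is always covered when treatment is on schedule, and a subject with about three weeks or less of maintenance is covered in full. This is a fair argument against giving the zero-coverage reading equal standing. It leaves most maintenance time uncovered in aggregate, and the literal words of 11.1 remain.

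The SAP also offers some looser wording. Section 11.2 says "Summary data by each treatment arm will be presented by but not limited to the following statistics", but that adds statistics and does not widen the definition of the events counted. The absence of a cutoff in 11.1 concerns the data included, and it specifies no maintenance AE table. SAP 11.1 sends visit-wise analyses to Table 2, which has a maintenance row, and SAP 6.0 plans changes from baseline for laboratory and vital-sign variables. This shows that the safety section is inconsistent, perhaps unfinished rather than deliberately narrowed. It does not supply AE or SAE rates.

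The DMC charter (SAP 14.1) keeps the committee in place through trial completion and lets its chair call further meetings, so another review is possible. None is planned. Maintenance safety at 400 mg BID is also a Phase 1 secondary objective, and Protocol 5.6.4 describes the dose as well characterised. That lowers the stakes but does not replace the randomized Phase 2 comparison.

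The person-time shares do depend on assumed medians. The 8.7-month case uses PFS from randomization as a stand-in for time on maintenance and ignores stopping for toxicity.

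**Conclusion.** The concern holds. The SAP replaces the protocol's AE and SAE window with a shorter one, does not say so, and leaves secondary objective 5 without AE or SAE rates for most or all of maintenance. The size depends on the reading: about 21 to 23 maintenance days are counted on schedule if the 30-day tail governs, and none if SAP 11.1 is taken literally. The 21-to-23-day figure rests on the assumed maintenance start, and a toxicity delay can remove almost all of it. The conflict between the two documents needs no assumption. The primary PFS analysis is not affected, all deaths are still counted, and blinded monitoring continues.

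**What to change.** In SAP 11.1 and 11.2, define treatment-emergent AEs and SAEs by onset from the first dose to 30 days after the last dose of study drug, including maintenance, as in Protocol 8.1.7.2. State which study drug sets the dates, because Protocol 8.1.7.2 means veliparib or placebo while SAP 6.0 also includes chemotherapy. The As-Treated population in SAP 5.1 can stay as it is.

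Two descriptive tables would help but are optional:

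- a maintenance-period table among subjects who started maintenance, without testing;
- a combination-period table ending at the first maintenance dose, or 30 days after the last dose for subjects who never start maintenance.

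At the same time, restore the three death categories of Protocol 8.1.7.4 and use one laboratory window across SAP 6.0, 11.1 and 11.4. Declare and justify any remaining departure from the protocol, as was done for ORR.

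The cost is SAP wording and table programming. Protocol 6.5 already collects AEs to 30 days after study drug is stopped, and SAP 12.0 describes unblinding as still to come.

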#### **8.1.7.5 Longitudinal Analyses of Laboratory and Vital Signs Data**

Changes from baseline will be analyzed for each scheduled post-baseline visit and for the final visit for blood chemistry and hematology parameters, as well as urinalysis and vital sign parameters. If more than one measurement exists for a subject on a particular day, an arithmetic average will be calculated. This average will be considered to be that subject's

measurement for that day. Post-baseline measurements more than 30 days after the last dose of randomized study drug will not be included. Subjects that do not have a baseline measurement or do not have any post-baseline measurements will not be included. For Phase 1, changes from baseline will be analyzed by dose level at each scheduled visit. For Phase 2, comparisons of the differences in mean changes from baseline between Arm A and Arm C as well as between Arm B and Arm C will be made using ANCOVA with treatment group as the factor and baseline as a covariate.

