#### **8.1.7.6 Analyses of Laboratory Data Using NCI CTCAE**

Where applicable, blood chemistry and hematology determinations will be categorized according to NCI CTCAE version 4.0 grades, and shifts from baseline NCI CTCAE version 4.0 grades to maximum and final post-baseline grades will be assessed. The baseline and final grades will be defined respectively as the grade of the last measurement collected prior to the first dose of study drug, and as the grade of the last post-baseline measurement collected no more than 30 days after the last dose of study drug. If multiple values are available for a post-baseline measurement, then the value with the highest NCI CTCAE grade will be used in the assessment of shift. Comparisons of the number of subjects experiencing a shift from baseline grades of 0 to 2 or no grade to maximum post-baseline grades of 3 to 4, and from baseline grades of 0 to 2 or no grade to final post-baseline grades of 3 to 4 between Arm A and Arm C as well as between Arm B and Arm C will be performed using Fisher's exact tests. Additional analyses including all measurements collected, regardless of the number of days after the last dose of study drug, will be performed.

Detailed listings of data for subjects experiencing NCI CTCAE Grade 3 to 4 blood chemistry and hematology values will be provided. All measurements collected, regardless of the number of days after the last dose of study drug, will be included in these listings.

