##### **Analyses of Shift from Baseline in Clinical Laboratory Data**

Where applicable, blood chemistry and hematology determinations will be categorized according to NCI CTCAE version 4.0 grades. The baseline and maximum grades are defined respectively as the baseline grade and as the highest (worst) grade during post-baseline visit on or prior to 30 days of last study drug. Section 6.0 describes the analysis convention for laboratory values used in summary of shift from baseline analyses. Baseline NCI CTCAE version 4.0 grades and maximum post-baseline grades, as well as shifts from baseline grade 0 - 2 to maximum grade 3 - 4, will be assessed by cross-tabulation for both chemistry and hematology. Shifts from baseline grade 0 - 2 to final grade 3 - 4 will be assessed by cross-tabulation for Proteinuria.

Detailed listings of all measurements collected in the extracted database for subjects experiencing NCI CTCAE Grade 3 to 4 blood chemistry and hematology values will be provided. All measurements collected, regardless of the number of days after the last dose of study drug, will be included in these listings.

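### SAP 11.1 removes, without a recorded reason, the between-arm safety comparisons that Protocol 8.1.7 specifies, and plans no between-arm estimate, interval or test of added toxicity in their place

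*SAP*

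**What the plan says.** **Protocol, Phase 2 safety methods.**

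- Section 8.1.7.2 plans "comparisons of the percentages of subjects experiencing an adverse event between Arm A and Arm C". It adds the B v C contrast and names the test: "Arm B and Arm C will be performed using Fisher's exact test".
- Section 8.1.7.3 carries this over: "Serious adverse events will be summarized using the same methods as adverse events described above".
- Section 8.1.7.5, on laboratory and vital-sign data, plans "comparisons of the differences in mean changes from baseline between Arm A and Arm C", again with B v C. These "will be made using ANCOVA with treatment group as the factor and baseline as a covariate".
- Section 8.1.7.6, on shifts from grade 0-2 (or no grade) to grade 3-4, says that comparisons between "Arm A and Arm C as well as between Arm B and Arm C will be performed using Fisher's exact tests".

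**Protocol synopsis.** Under Statistical Methods, Safety, Phase 2 safety is described only as descriptive statistics by treatment arm, with no mention of a test.

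**SAP.** Section 11.1 says: "There will be no statistical comparison for safety analysis unless otherwise specified". Section 11.2 lists numbers and percentages by arm, 11.3 summarises deaths, and in 11.4 the laboratory grade shifts "will be assessed by cross-tabulation for both chemistry and hematology". Section 6.0 keeps visit-wise change from baseline for laboratory and vital-sign parameters but names no between-arm model.

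**The concern.** The SAP describes itself in section 3.0 as elaborating the Protocol's statistical methods. Here it removes four of them. Where it departs from the Protocol on the response-rate period, it says so and gives a reason (SAP 4.1). It does neither for safety.

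The comparison matters because every arm receives carboplatin and etoposide. Myelosuppression is the main toxicity of that backbone (Protocol 3.4), and the Protocol expects veliparib's toxicity to overlap with it in nausea, vomiting and myelosuppression (3.7). The added toxicity of veliparib is therefore a difference from Arm C, the randomised placebo control. Safety of the veliparib combination is a secondary objective (Protocol 4.0, SAP 4.1). As the SAP stands, the report would show three columns of percentages and leave readers to subtract them, with no statement of how precise the difference is.

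**Working it through.** **Step 1: match each Protocol comparison to the SAP.**

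| Protocol comparison (A v C, B v C) | SAP counterpart | Between-arm estimate, interval or test in SAP |
|---|---|---|
| AEs, Fisher's exact (8.1.7.2) | 11.2: n and % by arm | None |
| SAEs, same methods (8.1.7.3) | 11.2: n and % by arm | None |
| Laboratory and vital-sign change, ANCOVA (8.1.7.5) | 6.0: visit-wise change from baseline | None |
| Shifts to grade 3-4, Fisher's exact (8.1.7.6) | 11.4: cross-tabulation | None |

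The exception clause in SAP 11.1 is never used in 11.2 to 11.4. Where the SAP wants ANCOVA it names it, as for ECOG status in 10.6.4. The Protocol's itemised list of changes (Appendix G) shows no change to 8.1.7.

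**Step 2: what the plan supplies for a calculation.** It gives no safety event rate, precision or power. Its only sample-size calculation is for PFS, which reproduces: 4 × (1.2816 + 0.8416)² / (ln 0.63)² = 84.5, so 85 events, with 80.2% power. This point does not depend on that figure. The one input taken from the plan is about 60 subjects per arm (Protocol 8.2, SAP 4.3).

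**Step 3: precision of a risk difference.** The control and veliparib event rates p_C and p_V are assumptions, chosen to span common and less common events. The 95% half-width is

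1.96 × √[p_C(1 − p_C)/n_C + p_V(1 − p_V)/n_V].

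For 50% v 70% at 60 v 60: 1.96 × √[(0.25 + 0.21)/60] = 0.172. For A+B pooled against C, at 120 v 60: 1.96 × √[0.25/60 + 0.21/120] = 0.151.

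**Step 4: power of the Protocol's test.** This is Fisher's exact test, by full enumeration, at two-sided 0.05. The level is also an assumption, since Protocol 8.1.7 states none for safety.

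| Assumed C v veliparib | Difference | Half-width 60 v 60 | Fisher power | Half-width 120 v 60 | Fisher power |
|---|---|---|---|---|---|
| 50% v 70% | 20 points | 17.2 | 54% | 15.1 | 71% |
| 20% v 40% | 20 points | 16.0 | 60% | 13.4 | 78% |
| 10% v 25% | 15 points | 13.3 | 49% | 10.8 | 67% |

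For a 10-point difference at 60 v 60, power is about 25% (10% v 20%) and 16% (30% v 40% or 50% v 60%).

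An observed 20-point excess at 60 per arm could therefore reflect a true excess of only a few points or one above 35 points (for 50% v 70%, 20 ± 17). Two percentages side by side do not show that range.

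**The case against.** The strongest reply is that little is lost. SAP 11.1 presents safety for each arm, including the randomised placebo-plus-chemotherapy arm. The A v C and B v C differences can be read from the tables, and a reader can compute an interval from n and %. SAP 11.2 also tabulates events related to veliparib/placebo, with causality recorded separately for each drug (Protocol 6.4). The Protocol synopsis itself calls Phase 2 safety descriptive. With power of 49% to 60% for differences of 15 to 20 points, a large set of unadjusted P values would be of doubtful use, and a purely descriptive safety report is a defensible choice at this size.

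Much of this stands. A reader might infer from SAP 11.1 that no planned safety analysis can separate veliparib's toxicity from that of carboplatin/etoposide, or that the shift tables show only change common to all arms. The documents do not support either reading. The tables and shifts are produced for Arm C too, so the common chemotherapy effect can be removed by comparison, and visit-wise changes and veliparib-related events are also kept.

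Three things survive. The synopsis line is a summary and does not cancel the specific methods in the body of the Protocol; it is a further inconsistency to settle. Attribution to a drug is made by blinded investigators (Protocol 5.5.6) and is weakest where toxicities overlap, so it does not replace the randomised contrast. Low power is an argument for intervals over P values. It does not justify giving neither.

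**Conclusion.** The point holds as an unexplained inconsistency between Protocol and SAP with a modest but real cost. All four Protocol comparisons lack a SAP counterpart, no reason is recorded, and no between-arm estimate, interval or test of added toxicity is planned for a secondary objective. Descriptive comparison with Arm C remains possible, and the primary PFS analysis is unaffected.

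The missing information is the precision of the difference. At about 60 per arm, 95% half-widths are roughly 13 to 17 points under the assumed rates, falling to about 11 to 15 points when A and B are pooled. These figures rest on assumed event rates, a 0.05 two-sided level and full enrolment. The textual finding rests on none of them. The change should be made; it is an improvement to reporting and does not correct an invalid analysis.

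**What to change.** In SAP 11.1, replace the sentence with:

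> For A vs C and B vs C (and A+B vs C in the combination period, where A and B receive the same regimen), risk differences with 95% CIs will be given for any TEAE, grade 3 or 4 TEAE, serious TEAE and laboratory shifts from grade 0-2 to grade 3-4. The Fisher's exact P values of Protocol 8.1.7.2, 8.1.7.3 and 8.1.7.6 will be shown as descriptive for A vs C and B vs C. Changes from baseline in laboratory values and vital signs will be compared by ANCOVA as in Protocol 8.1.7.5. No multiplicity adjustment is made.

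The SAP should say that the risk differences, their intervals and the pooled contrast are additions to the Protocol. SAP 11.2 counts events up to 30 days after the last combination-period dose, which can run into maintenance, where A and B differ. The pooled contrast should therefore state that it stops at the first maintenance dose.

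If the sponsor prefers no P values, record and justify that departure, as was done for the response-rate period, and still report the risk differences with CIs. The synopsis wording should be reconciled with Protocol 8.1.7 at the same time.

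The cost is SAP wording and some extra table programming, with no new data. The drawback is many unadjusted comparisons, some of which will look notable by chance. The descriptive label and the lead given to estimates over P values handle this.
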